6.4 Toxicity management guidelines

6.4.1 Durvalumab

Guidelines for the management of immune-mediated reactions, infusion-related reactions, and non-immune-mediated reactions for durvalumab are provided in the durvalumab Toxicity Management Guidelines (TMGs). Please see APPENDIX 1.

Patients should be thoroughly evaluated and appropriate efforts should be made to rule out neoplastic, infectious, metabolic, toxin, or other etiologic causes of the imAE. Serologic, immunologic, and histologic (biopsy) data, as appropriate, should be used to support an imAE diagnosis. In the absence of a clear alternative etiology, events should be considered potentially immune related.

In addition, there are certain circumstances in which durvalumab should be permanently discontinued (see section **Error! Reference source not found.** of this protocol and the Dosing Modification and Toxicity Management Guidelines in **Error! Reference source not found.**).

Following the first dose of IP, subsequent administration of durvalumab can be modified based on toxicities observed as described in the Dosing Modification and Toxicity Management Guidelines in **Error! Reference source not found.** These guidelines have been prepared to assist the Investigator in the exercise of his/her clinical judgment in treating these types of toxicities. These guidelines apply to AEs considered causally related to durvalumab monotherapy by the reporting investigator.

Dose reductions are not permitted. In case of doubt, the Investigator should consult with the Company.

All toxicities will be graded according to NCI CTCAE, Version5.0.

6.4.2 Sirolimus

Table 2 Criteria for interruption and re-initiation of Sirolimus

Stomatitis	Description	Management/Next Dose for Sirolimus
Grade 1	Minimal symptoms, normal diet	No modifications necessary. Manage with non-alcoholic or salt water (0.9%) mouth wash several times a day
Grade 2	Symptomatic but can eat and swallow modified diet	Manage with topical analgesic mouth treatments (e.g. benzocaine, menthol or phenol) with or without topical corticosteroids (i.e. triamcinolone oral paste)
Grade 3	Symptomatic and unable to adequately aliment or hydrate orally	Temporary dose interruption until recovery to grade ≤ 1 . Manage with topical analgesic mouth treatments (e.g. benzocaine, menthol or phenol) with or without topical corticosteroids (i.e. triamcinolone oral paste)
Grade 4	Symptoms associated with life-threatening consequences	Discontinue Sirolimus and treat with appropriate medical therapy.

*Patients requiring a delay of >2 weeks should go off protocol therapy.

Other Non-hematologic toxicities	Management/Next Dose for Sirolimus
\leq Grade 1	If toxicity is tolerable, no dose adjustment required. Initiate appropriate medical therapy and monitor.
Grade 2	If toxicity is tolerable, no dose adjustment required. Initiate appropriate medical therapy and monitor. If toxicity becomes intolerable, temporary dose interruption until recovery to grade ≤ 1 . Re-initiate sirolimus at the same dose. If toxicity recurs at grade 2, interrupt sirolimus until recovery to grade ≤ 1 . Re-initiate sirolimus at the same dose.

Other Non-hematologic toxicities	Management/Next Dose for Sirolimus
Grade 3	Temporary dose interruption until recovery to grade ≤ 1 . Initiate appropriate medical therapy and monitor. Consider re-initiating sirolimus. If toxicity recurs at grade 3, consider discontinuation.
Grade 4	Discontinue sirolimus and treat with appropriate medical therapy.

*Patients requiring a delay of >2 weeks should go off protocol therapy.

Hematologic Toxicities (anemia, neutropenia, thrombocytopenia)	Management/Next Dose for Sirolimus
\leq Grade 1	No change in dose
Grade 2	Hold until \leq Grade 1. Resume at same dose.
Grade 3	Hold until $<$ Grade 2. Resume at same dose. *
Grade 4	Off protocol therapy

* Patients who develop grade 3 neutropenia associated with temperature higher than 38.3 C should go off protocol therapy. Patients requiring a delay of >2 weeks should go off protocol therapy

6.4.3 Potential Overlapping Toxicites

Based on the pharmacological properties of a large monoclonal antibody and oral small molecule inhibitor, there are not anticipated overlapping toxicities.

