1.1.2 Potential role of mTOR inhibition in NSCLC and immunologic effects

Date: **11 February 2022**

Pharmacological inhibition of the mTOR pathway can modulate both innate and adaptive immunity. Modulation of the innate immune system by mTOR inhibition can be seen in the known inflammatory side effects including fever, pneumonitis, anemia of inflammation as well as the promotion of inflammatory cytokines IL-1B and IL-12²⁵. Rapamycin has been shown to decrease plasmacytoid dendritic cell production of interferon²⁶. Additionally, there is accumulating understanding of rapamycin and rapalogs impact on T cell activation and differentiation. Using a well described mouse model, Araki et al. showed increased numbers of virus specific memory CD8 T-cells following treatment with rapamycin. Low doses of rapamycin led to increased numbers of memory T cell precursors and regulation of memory T cell differentiation occurs through the mTORC1 pathway²⁷. The mTOR pathway is involved in the regulation of FOXP3 expression in regulatory T cells^{28, 29}. In a study of metastatic RCC patients on everolimus, better clinical responses were seen in patients that developed high expression of tumor specific Th1 cells and lower regulatory T cells (Tregs)³⁰.

The interaction of mTOR inhibition with PD-1/PDL-1 pathway has been studied in preclinical models. In genetically engineered mouse models of lung cancer, mTOR inhibition led to decreased tumor growth, increased tumor-infiltrating lymphocytes (TILSs) and decreased Tregs³¹, but there is some controversy over the mechanism. In that paper mTOR activation reportedly up-regulated PD-L1 while mTOR pathway inhibition with rapamycin decreased PD-L1³¹. A subsequent study using a murine model of RCC and human RCC cells showed that everolimus in combination with anti-PDL1 therapy up-regulated PD-L1 on the cell surface, indicating this mechanism underlies the therapeutic benefit of combination therapy³². Additionally, rapamycin was shown to enhance anti-PD-L1 treatment with durable tumor control in an immunogenic model of oral cavity cancer³³. These preclinical studies provide evidence of significantly enhanced antitumor activity with combined mTOR plus PD-1/PD-L1 targeted therapy over single agent immunotherapy in 3 different solid tumor models (RCC, NSCLC, and oral cancer).

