1.6.2 Overall risks

Monoclonal antibodies directed against immune checkpoint proteins, such as programmed cell death ligand 1 (PD-L1) as well as those directed against programmed cell death-1 (PD-1) or cytotoxic T-lymphocyte antigen-4 (CTLA-4), aim to boost endogenous immune responses directed against tumor cells. By stimulating the immune system however, there is the potential for adverse effects on other tissues.

Most adverse drug reactions seen with the immune checkpoint inhibitor class of agents are thought to be due to the effects of inflammatory cells on specific tissues. These risks are generally events with a potential inflammatory or immune mediated mechanism and which may require more frequent monitoring and/or unique interventions such as immunosuppressants and/or endocrine therapy. These immune mediated effects can occur in nearly any organ system,

Clinical Study Protocol

Investigational Drug Substance: MEDI4736 Sirolimus (Rapamune)

Study Number **19-20015**

Edition Number: 4

Date: **11 February 2022**

and are most commonly seen as gastrointestinal AEs such as colitis and diarrhea, pneumonitis/interstitial lung disease (ILD), hepatic AEs such as hepatitis and liver enzyme elevations, skin events such as rash and dermatitis and endocrinopathies including hypo- and hyper-thyroidism.

Neo-adjuvant studies additionally pose the risk of delaying or preventing surgery due to treatment related toxicities that may make surgery not feasible. Neoadjuvant PD-1 pathway targeting therapies have not significantly precluded surgery in ongoing single agent studies. Furthermore, neoadjuvant everolimus was well tolerated prior to surgery in NSCLC and neoadjuvant sirolimus was well tolerated prior to surgery in head and neck squamous cell carcinoma patients. However, the risks of combination durvalumab and sirolimus are not known. The dose limiting toxicity assessment of combination therapy portion of this study must be completed as outlined in section 5.1. Furthermore, a low dose of sirolimus, which corresponds to the target immunologic dose, will be administered.

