1.6.2.1 Risk associated with durvalumab

Risks with durvalumab include, but are not limited to, diarrhea/colitis pneumonitis/ILD, endocrinopathies (hypo- and hyper-thyroidism, type I diabetes mellitus, hypophysitis and adrenal insufficiency) hepatitis/increases in transaminases, nephritis/increases in creatinine, pancreatitis/increases in amylase and lipase, rash/pruritus/dermatitis, myocarditis, myositis/polymyositis, other rare or less frequent inflammatory events including neurotoxicities, infusion-related reactions, hypersensitivity reactions, and infections/serious infections.

For information on all identified and potential risks with durvalumab please always refer to the current version of the durvalumab IB. Further information on these risks can be found in the current version of the durvalumab IB.

In monotherapy clinical studies AEs (all grades) reported very commonly ($\geq 15\%$ of patients) are fatigue, nausea, decreased appetite, dyspnea, cough, constipation, diarrhea, vomiting, back pain, pyrexia, asthenia, anemia, arthralgia, peripheral edema, headache, rash, and pruritus. Approximately 9.4% of patients experienced an AE that resulted in permanent discontinuation of durvalumab and approximately 6.5% of patients experienced an SAE that was considered to be related to durvalumab by the study investigator.

The majority of treatment-related AEs were manageable with dose delays, symptomatic treatment, and in the case of events suspected to have an immune basis, the use of established treatment guidelines for immune-mediated adverse events (Appendix 1)

A detailed summary of durvalumab monotherapy AE data can be found in the current version of the durvalumab IB.

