1.6.2.2 Risk associated with Sirolimus

The safety profile of sirolimus differs based on indication (renal transplant or lymphangioleiomyomatosis) and goal trough range. As there are added complicating medical factors in the post-transplant population, detailed below are the reported side effects in patients with lymphangioleiomyomatosis.

Safety was assessed in a controlled trial involving 89 patients with lymphangioleiomyomatosis, 46 of whom were treated with Rapamune. The adverse drug reactions observed in this trial were consistent with the known safety profile for renal transplant patients receiving Rapamune, with the addition of weight decreased which was reported at a greater incidence with Rapamune when compared to placebo. Adverse reactions occurring at a frequency of $\geq 20\%$ in the Rapamune treatment group and greater than placebo include stomatitis, diarrhea, abdominal pain, nausea, nasopharyngitis, acne, chest pain, peripheral edema, upper respiratory tract infection, headache, dizziness, myalgia, and hypercholesterolemia.

Additional warnings and precautions in the FDA package insert based on clinical trials and post marketing experience include but are not limited to the following:

- **Increased Susceptibility to Infection and the Possible Development of Lymphoma:**

Increased susceptibility to infection and the possible development of lymphoma and other malignancies, particularly of the skin, may result from immunosuppression. Exposure to sunlight and ultraviolet (UV) light should be limited by wearing protective clothing and using a sunscreen with a high protection factor. Oversuppression of the immune system can also increase susceptibility to infection, including opportunistic infections such as tuberculosis, fatal infections, and sepsis.

- **Lung Transplantation Patients– Bronchial Anastomotic Dehiscence**

Cases of bronchial anastomotic dehiscence, most fatal, have been reported in de novo lung transplant patients when Rapamune has been used as part of an immunosuppressive regimen.

- **Hypersensitivity Reactions:**

Date: **11 February 2022**

Hypersensitivity reactions, including anaphylactic/anaphylactoid reactions, angioedema, exfoliative dermatitis and hypersensitivity vasculitis, have been associated with the administration of Rapamune

- **Angioedema:**

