Cases of interstitial lung disease [ILD] (including pneumonitis, bronchiolitis obliterans organizing pneumonia [BOOP], and pulmonary fibrosis), some fatal, with no identified infectious etiology have occurred in patients receiving immunosuppressive regimens including Rapamune. In some cases, the ILD was reported with pulmonary hypertension (including pulmonary arterial hypertension [PAH]) as a secondary event. In some cases, the ILD has resolved upon discontinuation or dose reduction of Rapamune. The risk may be increased as the trough sirolimus concentration increases.

Additional risks that pertain to the renal transplant population include declines in renal function, proteinuria, increased risk of calcineurin associated thrombotic microangiopathy, and additional opportunistic infections such as PCP and latent viral infections with BK or others. Please refer to full prescribing information in the FDA package insert.

Absorption

“The mean time to peak concentration after ingestion of the oral solution is approximately 1 hour and 2 hours in healthy subjects and renal transplant patients, respectively. The systemic availability of sirolimus is low, and was estimated to be approximately 14% after the administration of Rapamune Oral Solution. In healthy subjects, the mean bioavailability of sirolimus after administration of the tablet is approximately 27% higher relative to the solution. Sirolimus tablets are not bioequivalent to the solution; however, clinical equivalence has been demonstrated at the 2 mg dose level. To minimize variability in sirolimus concentrations, both Rapamune Oral Solution and Tablets should be taken consistently with or without food.”

Distribution

“The mean (\pm SD) blood-to-plasma ratio of sirolimus was 36 ± 18 in stable renal allograft patients, indicating that sirolimus is extensively partitioned into formed blood elements. The mean volume of distribution (V_{ss}/F) of sirolimus is 12 ± 8 L/kg. Sirolimus is extensively bound (approximately 92%) to human plasma proteins, mainly serum albumin (97%).”

Metabolism

“Sirolimus is a substrate for both CYP3A4 and P-gp. Sirolimus is extensively metabolized in the intestinal wall and liver and undergoes counter-transport from enterocytes of the small intestine into the gut lumen. Inhibitors of CYP3A4 and P-gp increase sirolimus concentrations. Inducers of CYP3A4 and P-gp decrease sirolimus concentrations.”

Excretion

Date: **11 February 2022**

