The dose of sirolimus chosen for this study is based on our pre-clinical data that indicate that a lower dose is most likely to result in the desirable pharmacodynamics effects on the immune system. For clinical use in the renal transplant setting and high immunologic risk transplants, sirolimus is recommended at an initial loading dose of 15 mg followed by 5mg/day maintenance, with adjustments based on trough level. In lymphangiomyomatosis (LAM), the recommended dose is 2 mg daily to block mTOR pathway activation; median whole blood

Date: **11 February 2022**

sirolimus trough concentration after 3 weeks of receiving sirolimus tablets at a dose of 2 mg/day was 6.8 ng/mL (interquartile range 4.6 to 9.0 ng/mL; n = 37). As the sirolimus treatment phase will be only 3 weeks, a single loading dose of 6mg on day 1 will be followed by 2mg daily. No dose changes will be made for individual patients given this short term low dose regimen designed to reach levels of 5-15 ng/ml, which was noted in pre-clinical studies to correlate with proliferation of memory T cells. This lower dose is also likely to be tolerated better by patients.

As an added safety measure, the first 6 patients will be monitored through hospital discharge following surgical resection to assess for dose limiting toxicities (DLTs) related to sirolimus followed by durvalumab therapy. DLTs and safety analysis are described in section 6.4.

Patients will be closely monitored for safety and tolerability throughout the study. Safety assessments will include collection and monitoring of adverse events and laboratory abnormalities graded per the National Cancer Institute Common Terminology Criteria for Adverse Events, Version 5.0 (NCI CTCAE v5.0). Tumor tissue samples, normal lung parenchyma, whole blood samples, and optional lymph node samples will be collected for biomarker assessments.

After study treatment discontinuation, patients will be followed per SOC, but information on recurrence and survival will be collected every 6 months for up to 2 years after the last patient receives the last dose in the study (in person or by phone). Patients who discontinue the study due to adverse events will be followed until resolution or stabilization of the adverse event. Appropriate dose modifications are described in Section 6. No investigational or commercial agents or therapies other than those described below may be administered with the intent to treat the patient's malignancy.

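### Section 6.4.3 anticipates no overlapping toxicities although pneumonitis/ILD is listed for both drugs; Table 2 permits sirolimus through tolerable Grade 2 pneumonitis, and the guideline scope over the lead-in is inconsistent

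*Combined protocol and SAP*

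**What the plan says.** **Shared toxicity.** Section 6.4.3 consists of one sentence: "Based on the pharmacological properties of a large monoclonal antibody and oral small molecule inhibitor, there are not anticipated overlapping toxicities". Section 1.6.2 is more cautious: "However, the risks of combination durvalumab and sirolimus are not known".

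**Risk lists.** For durvalumab, 1.6.2.1 says: "Risks with durvalumab include, but are not limited to, diarrhea/colitis pneumonitis/ILD". Section 10.2.3 also lists pneumonitis/ILD as an adverse event of special interest. For sirolimus, 1.6.2.2 describes ILD cases, "some fatal, with no identified infectious etiology have occurred in patients receiving immunosuppressive regimens including Rapamune", and adds: "In some cases, the ILD has resolved upon discontinuation or dose reduction of Rapamune". The background in 1.1.2 makes the same link for the drug class: "mTOR inhibition can be seen in the known inflammatory side effects including fever, pneumonitis".

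**Sirolimus rules.** Table 2 in 6.4.2 has three blocks: stomatitis, other non-hematologic toxicity and hematologic toxicity. None names pneumonitis or ILD. In the other non-hematologic block, a Grade 2 event needs no change in dose while it is tolerable; if it becomes intolerable, sirolimus is interrupted until Grade 1 or less. In the hematologic block, any Grade 2 event requires a hold. Section 3.1 removes dose reduction as an option: "No dose changes will be made for individual patients given this short term low dose regimen".

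**Guidelines.** Sections 10.1.6 and 10.2.3 direct suspected pneumonitis/ILD to the Appendix 1 toxicity guidelines without limiting this to a drug or phase. Section 6.4.1 restricts the guidelines to events attributed to durvalumab monotherapy; 10.2.3 extends them to events attributed to the study drug or regimen.

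**The concern.** Safety of the sequence is a co-primary objective (2.1), and these patients are about to undergo lung resection. Section 1.6.2 itself warns that treatment toxicity could delay or prevent surgery. Pneumonitis is the shared toxicity that matters most here, and 6.4.3 tells investigators to expect none.

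The practical difficulty arises on days 1 to 21, before any durvalumab. For a tolerable Grade 2 pneumonitis in that period, Table 2 asks for no interruption, 10.1.6 says to apply the Appendix 1 guidelines, and 6.4.1 confines those guidelines to events that cannot yet have occurred. Two investigators, each following the text, could handle the same event differently.

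**Working it through.** The plan states no figure on this point, so the check is mainly a comparison of sections, with three short calculations to give size.

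**1. Is 6.4.3 consistent with the risk text?**

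| Toxicity | Durvalumab | Sirolimus |
|---|---|---|
| Pneumonitis/ILD | 1.6.2.1, 10.2.3 | 1.1.2, 1.6.2.2 |
| Diarrhea | 1.6.2.1 | 1.6.2.2: "in the Rapamune treatment group and greater than placebo include stomatitis, diarrhea" |
| Infection | 1.6.2.1 | 1.6.2.2 |
| Hypersensitivity | 1.6.2.1 | 1.6.2.2 |

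It is not. Sequential dosing does not rescue the sentence, because it argues from the type of molecule and not from timing. Exposure also overlaps. The last sirolimus dose is on day 21 and durvalumab starts on day 22 (8.1.2). Section 1.6.2.2 gives a terminal half-life of 62 ± 16 hours, measured in stable renal transplant patients. With first-order decay, the fraction remaining after t hours is 0.5^(t/62):

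- 24 hours: 0.765 (0.70 to 0.81 for half-lives of 46 to 78 hours)
- 7 days: 0.153 (0.08 to 0.23)
- five half-lives: 5 × 62 / 24 = 12.9 days (9.6 to 16.2)

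**2. What does Table 2 do with Grade 2 pneumonitis?** It is non-hematologic and not stomatitis, so the generic row applies: no interruption is required if the event is tolerable. Grades 3 and 4 already lead to interruption or discontinuation, so the gap is at Grade 2. The dose-limiting toxicity criteria in 6.3 do count Grade 2 pneumonitis that fails to resolve within 3 days of maximal supportive care, but that window opens at the first durvalumab dose and omits the lead-in.

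Upper bound on further exposure if a case is recognised on day d and dosing continues to day 21: 21 − d doses of 2 mg.

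- Day 8: 21 − 8 = 13 doses, 26 mg
- Day 15: 21 − 15 = 6 doses, 12 mg

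The planned course totals 6 + 20 × 2 = 46 mg, so these are 26/46 = 57% and 12/46 = 26% of it. The two days are illustrations, not scheduled visits.

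**3. Do the guidelines reach the lead-in?** Under 10.1.6 and 10.2.3, yes. Under the scope sentence in 6.4.1, no, since an event before the first durvalumab dose cannot be caused by durvalumab. Section 6.4.1 also allows durvalumab to be modified after the first dose of investigational product, and Table 11 (15.1) lists sirolimus as one. So 6.4.1 can be read both ways.

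**4. How often might the rule be needed?** The documents give no rate of Grade 2 pneumonitis over a three-week sirolimus course. With assumed rates p in 31 patients, the expected number is 31p and the chance of at least one is 1 − (1 − p)^31:

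| Assumed p | Expected cases | At least one |
|---|---|---|
| 1% | 0.31 | 27% |
| 3% | 0.93 | 61% |
| 5% | 1.55 | 80% |

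**The case against.** The strongest reply is that the protocol already handles pneumonitis. Section 10.1.6 is specific, strongly recommends a full work-up, and makes the principal investigator responsible for staff knowing it. Section 10.2.3 adds tests when pneumonitis is suspected on study treatment, which by Table 1 includes sirolimus. Section 4.3 requires stopping for intolerable toxicity from either drug or when safety is at risk, and 8.1 allows durvalumab to be delayed. Section 6.4.1 tells investigators in doubt to consult the company. Section 4.2 excludes patients with prior or active pneumonitis. The sirolimus dose is low and short, and 1.6.2.2 links ILD risk to trough level.

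All of that stands, and it rules out three stronger inferences a reader might draw:

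- That Table 2 orders sirolimus to continue. It only says no change is required, so a hold is allowed and the dose counts are upper bounds.
- That the lead-in has no pneumonitis guidance or no means of stopping. It has both.
- That Appendix 1 lacks a suitable hold. Its content is not in the text reviewed. Its listed title refers to MEDI4736 therapy, so nothing seen shows that it alters the sirolimus rule, but that is weak evidence either way.

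It is also fair that a Table 2 hold cannot manage co-exposure after day 21, when sirolimus is finished. The 6.4.3 sentence and the Table 2 row are separate matters. The link is only that a hold with a recovery condition governs whether durvalumab starts while a lung event is unresolved.

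None of this reconciles 6.4.3 with 1.6.2, or 6.4.1 with 10.2.3, or explains why Grade 2 anemia requires a hold and Grade 2 pneumonitis does not.

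**Conclusion.** The point holds and should be fixed. Section 6.4.3 contradicts the protocol's own risk text; this follows from the wording alone and needs no assumption. Table 2 permits sirolimus to continue through tolerable Grade 2 pneumonitis, and the two scope sentences disagree on whether the guidelines cover the lead-in. The defect lies in the written rule and its scope. It is not an absence of clinical discretion.

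The size is modest. Continued exposure is at most 13 or 6 doses for recognition on day 8 or 15. On the assumed rates, the rule may be needed for no patient or for one or two. The case rests on the seriousness of an event the protocol describes as sometimes fatal, in patients awaiting lung surgery. No sample size, error rate or power figure is affected.

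**What to change.** 1. Replace the 6.4.3 sentence with the toxicities that 1.6.2 lists for both drugs: pneumonitis/ILD first, then diarrhea, infection and hypersensitivity.
2. Add a pneumonitis/ILD row to Table 2. Hold sirolimus at Grade 2 or higher, including while a suspected case is worked up under 10.1.6. Require recovery to Grade 1 or less, the level the table already uses for interrupted non-hematologic toxicity, before durvalumab cycle 1. Word the row to agree with Appendix 1 and keep the existing rule that a delay of more than 2 weeks ends protocol therapy.
3. Change the scope sentence in 6.4.1 to match 10.2.3.

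The cost is two sentences and one table row in an amendment, with the IRB review that 12.4 requires if it is judged to affect safety significantly. It adds no visits or samples. The downside is an occasional sirolimus interruption or a delay to durvalumab or surgery, sometimes for a suspected case that proves not to be pneumonitis. Rarely, a patient may go off therapy before durvalumab. That patient leaves the efficacy population (11.1.2) and is not replaced unless consent was withdrawn (4.4).
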